4.0 PROPOSAL

We will investigate in a prospective, longitudinal, observational, multi-institutional study the frequency of receiving allogeneic HCT among patients with AML or MDS considered for induction therapy at multiple institutions. Our primary goal here is to investigate how often older and medically infirm AML patients are referred to undergo allogeneic HCT. We will collect data on outcome-discriminative criteria, such as age, intensity of induction treatment, performance status, cytogenetic risks, and high white blood; in addition to data on patients and physician attitudes towards decision-making style and choice of therapy, socio-demographic variables, and baseline QOL to assess reasons patients may not be offered allogeneic HCT. We will evaluate differences between patients who receive versus those who do not receive allogeneic HCT by comparing the previously mentioned characteristics.

We would like also to understand who benefits from allogeneic HCT and to provide better tools for identifying these patients. Conversely, it is also important to identify patients for whom allogeneic HCT is not recommended because of relatively high treatment-related morbidity and mortality. Other important considerations in these judgments are the toxicity of treatment and the QOL experienced by survivors of either treatment approach. We will observe the two groups of patients who will be treated with allogeneic HCT or conventional therapy over 24 months. Outcome comparisons will be carefully adjusted for differences between patients in comorbidities and outcome-discriminative criteria, socio-demographic factors, decision-making preferences, and baseline QOL scores, which were collected at baseline assessment. These data will help individualize future treatment recommendations.

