In order to address these limitations, the CCI was modified in a way that better detected comorbidities among HCT recipients [74]. First, the definitions of several comorbidities were modified by adding progressive impairments of diffusion capacity of carbon monoxide (DLCO) and/or forced expiratory volume in 1-second (FEV1), left ventricular ejection fraction (LVEF) of $\leq 50\%$, and progressive elevations of levels of bilirubin and hepatic transaminases to the clinical definitions of pulmonary, cardiac, and hepatic comorbidities, respectively. In addition, new cut-offs for serum creatinine levels were set to better define renal comorbidity. Second, all comorbidities encountered in transplanted patients were included in the risk assessment analysis.

Protocol 2368.00

The study included 1055 patients with different hematological diseases who were given allogeneic HCT after nonmyeloablative (n=249) or myeloablative (n=761) conditioning. Two thirds of the patients were randomly assigned to a training set and one third to a validation set. Integer weights of comorbidities were calculated based on adjusted HRs from Cox proportional hazard models of 2-year NRM. The new HCT-CI included 17 comorbidities acquiring scores from 1 to 3.

In the training set, HCT-CI scores of 0, 1, 2, 3, ≥ 4 predicted 2-year NRM of 9%, 14%, 27%, 41%, and 43%, respectively. In the validation set, HCT-CI scores showed higher sensitivity than the CCI scores in capturing comorbidities. HCT-CI scores of 1-2 and ≥ 3 were found in 34% and 28% of patients, while only 10% and 3% of patients had CCI scores of 1 and ≥ 2 , respectively. The HCT-CI scores of 0, 1-2, and ≥ 3 showed good discrimination of NRM (14%, 21%, and 41%) and survival (71%, 60%, and 34%), respectively (**Figure 2**).

The discriminatory capacity of the HCI-CI and CCI, defined as the ability of the model to separate those patients who survived from those who died, were compared using the *c*-statistic or concordance index [75], which was identical to the area under a receiver operating characteristic curve (AUC). A *c*-statistic value of 1.0 indicated perfect predictive discrimination and a value of 0.5 indicated no ability to discriminate. The HCT-CI scores showed higher discriminative power than the CCI scores both for NRM (*c*-statistic of 0.692 versus 0.546, $P < 0.001$) and survival (*c*-statistic of 0.661 versus 0.561, $P < 0.001$).

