For the comparison study, power calculations are complicated by the time-dependent nature of the treatment groups, as well as by likely non-proportionality in the hazard ratio for HCT. Were these factors not present, the expected 170 patients undergoing HCT compared to 505 who do not undergo HCT, would provide at least 80% power to detect an increase in OS of 13%, at the 2-sided 0.05 level of significance. Because of the large number of unknown assumptions it is nearly impossible to estimate the true power for the actual analysis that will be done, other than that the detectable effect size is likely considerably larger than 13%. Nevertheless, based on previous experience with time-dependent analyses (such as of chronic graft-versus-host disease after HCT),[107] the overall sample size should be sufficient to detect effects of meaningful clinical magnitude.

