(iii) Given the expected bias in treatment selection and to further enhance our ability of obtaining accurate statistical inferences, we will use propensity scores. Propensity scores will estimate the probability on the basis of all patients and center characteristics that patients would proceed to allogeneic HCT with the use of proportional hazard model to adjust for between-group differences in the previously mentioned characteristics.[112] The magnitude of divergence of propensity scores between the two approaches will allow us to assess the amount of bias in treatment selection. Inverse-probability-weighting based on the propensity score will then be used as a secondary tool to adjust for differences between the two treatment-groups [113]. This approach will be implemented to create balance and it involves weighting each patient who received HCT by the inverse of the probability that he or she would be selected for HCT and weighting each patient who received conventional treatment by the inverse of the probability that he or she would be selected for conventional treatment. We will verify the performance of the propensity model by comparing the distribution of covariates and propensity scores between treatment groups both before and after inverse probability weighting.[114] Adjusted OS curves will be estimated using the inverse-probability-weighting approach of Cole and Hernan.[115] Assessment of benefit of either approach will be done in quintiles of propensity scores.

(iv) Sensitivity analyses will be performed to better understand any statistical disagreement between the models. First, OS curves for comparing both groups will be estimated using a double robust strategy of combining the inverse-probability weighting with the regression-based estimation [116]. Secondly, propensity scores will be used to construct matched samples from both groups to be used for simple matched pair analyses which adjust for confounding variables. Finally, we will use the method of Lin et al [117] to assess whether the observed differences in the rate of death could be due to an unmeasured confounder.

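### Section 4.0 wants to know who benefits from HCT, but section 11.3 plans no estimate of the HCT effect by baseline clinical profile

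*Combined protocol and SAP*

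**What the plan says.** Section 4.0 (Proposal) sets three related hopes. The first is "We would like also to understand who benefits from allogeneic HCT and to provide better tools for identifying these patients". The second is "Conversely, it is also important to identify patients for whom allogeneic HCT is not recommended", because of treatment-related morbidity and mortality. The third is a use: "These data will help individualize future treatment recommendations".

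Section 11.3 compares HCT with conventional therapy in the older or medically infirm cohort:

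- 11.3(2)(i): HCT is a time-dependent covariate in models for NRM, OS and DFS. Comorbidities, disease response, age, QOL, socio-demographic variables, preferences and institution are adjusters. The HCT hazard ratio may change with time since transplant.
- 11.3(2)(ii): landmarks at 3, 6 and 9 months, and interval hazards for patients not transplanted, early after transplant and late after transplant.
- 11.3(2)(iii): propensity scores and inverse-probability weighting, then "Assessment of benefit of either approach will be done in quintiles of propensity scores".
- 11.3(2)(iv): doubly robust, matched and unmeasured-confounder analyses.

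On size, section 11.1 says that "the expected 170 patients undergoing HCT compared to 505 who do not undergo HCT", setting aside time-dependence and non-proportionality, "would provide at least 80% power to detect an increase in OS of 13%, at the 2-sided 0.05 level of significance". It then warns that "the detectable effect size is likely considerably larger than 13" per cent.

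**The concern.** Learning who benefits means estimating how the HCT effect differs between kinds of patient. Nothing in section 11.3 does that. A covariate used as an adjuster shifts a patient's baseline risk but leaves the HCT effect the same for everyone. Letting the effect vary by time after transplant shows when risk rises or falls, not in whom.

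The propensity score is built from all patient and center characteristics. A given quintile therefore mixes age, comorbidity, disease features, preferences and site. A result in, say, the third quintile cannot be turned into a description of a patient.

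The cohort is also mixed by design. Under section 11.1 it joins patients aged 60 or over with any comorbidity score to younger patients with scores of 3 or more. If the HCT effect does differ within it, an average could hide that. Any later statement about who benefits would then rest on subgroups chosen after seeing the data.

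**Working it through.** **1. Is there any analysis by clinical profile?** Going through the plan item by item:

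- 11.2 models who receives HCT, not who benefits.
- 11.3(2)(i) and (ii) allow variation by time and transplant state only.
- 11.3(2)(iii) and (iv) re-estimate the same overall contrast, apart from the quintile split.
- 11.3(4) contains the only prediction model in section 11, and it concerns ICU mortality.
- Objective 5.2.1.3 (effect of pulmonary function tests and biomarkers on the HCT comparison) is the nearest to effect modification. Section 8.1.3 collects these at one site only, and section 11 gives no matching analysis.

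There is no HCT-by-covariate term and no subgroup by age, HCT-CI, cytogenetic risk or disease response.

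**2. The plan's own power figure.** Inputs from 11.1: 170 versus 505, +13 points in OS, two-sided 0.05. Comparison OS is not given, so it was varied from 5% to 85%. The lowest power is at about 44.5% versus 57.5%:

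- pooled proportion = (170 × 0.575 + 505 × 0.445)/675 = 0.478
- null SE = √[0.478 × 0.522 × (1/170 + 1/505)] = 0.0443
- alternative SE = √[0.575 × 0.425/170 + 0.445 × 0.555/505] = 0.0439
- power = Φ[(0.13 − 1.96 × 0.0443)/0.0439] = Φ(0.98) = 83.7%

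The claim of at least 80% is reproduced for the overall contrast.

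**3. Power for a difference in benefit.** Take a two-level modifier with prevalence q, equal in both treatment groups. Then SE(interaction) = SE(main)/√[q(1 − q)]. Assumptions: comparison OS 20-50%, and q 25-50%.

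- Example at comparison OS 30%: SE(main) = √[0.43 × 0.57/170 + 0.30 × 0.70/505] = 0.0431. At q = 0.5, SE(interaction) = 0.0862, and power for 13 points = Φ(0.13/0.0862 − 1.96) = 33%. At q = 0.25, the SE is 0.0995 and power is 26%.
- Over the full range, the interaction SE is 2.0-2.3 times the main-effect SE. Power for a 13-point difference in benefit is 25-37%. The smallest difference detectable with 80% power is 22.5-28.5 points.

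**4. The same on the hazard scale.** With D deaths and HCT share a = 170/675 = 0.252, SE = 1/√[D·a(1 − a)·q(1 − q)], and the detectable ratio of hazard ratios is exp(2.80 × SE). D is assumed to be 400-480.

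- D = 480, q = 0.5: SE = 0.210, ratio 1.80
- D = 400, q = 0.25: SE = 0.266, ratio 2.11

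**5. Propensity quintiles.** An average quintile has 170/5 = 34 HCT and 505/5 = 101 other patients. For comparison OS of 20-50%, power for 13 points is 25-35%, and the detectable difference is 25-27 points. In a low quintile with an assumed 13 HCT and 122 other patients, it is 36-39 points. Quintiles therefore answer a less useful question and are no more precise.

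**6. Cohort structure.** By 11.1, about 500 of 670 patients are 60 or over, and the other 170 are younger with scores of 3 or more. No patient under 60 has a score of 0-2. An HCT by age contrast across age 60 can be estimated only within scores of 3 or more, and an HCT by HCT-CI contrast partly reflects age.

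**The case against.** The strongest reply is that the unmet aim is not an objective. Section 4.0 says the investigators would like to understand who benefits, and individualized recommendations are a hoped-for later use. No numbered objective in section 5 asks the question. Objective 5.1.2 is an overall comparison, and 11.3 analyses it. This stands as a limit on the point: the plan does what its numbered objectives ask. It does not explain how the hope in 4.0 would be met.

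It is also fair that the plan does not force one constant HCT effect, since it allows variation by time after transplant. What is missing is variation by baseline profile.

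A reader might infer from section 3.7 that HCT helps patients with low scores and harms those with high ones. HCT-CI groups 0, 1-2 and 3 or more there "showed good discrimination of NRM (14%, 21%, and 41%) and survival (71%, 60%, and 34%), respectively". If survival without HCT is assumed to be 45% in every group, hazard ratios of 0.43, 0.64 and 1.35 follow, with a ratio of about 3.2 between the extremes. The documents do not support this:

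- The ratio is ln(0.34)/ln(0.71) = 3.15. It uses HCT recipients only, and the assumed 45% cancels, so trying other common values tests nothing.
- Section 3.1 reports that comorbidity predicts survival across cancer types. If it worsens survival without HCT to the same degree on the hazard scale, the ratio is 1.
- The source cohort had mixed hematological diseases and mostly myeloablative conditioning (761 versus 249).

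Those figures show prognosis after HCT, not effect modification.

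Low power is a further objection to adding interaction tests. It is a reason to report estimates with intervals as exploratory. It is not a reason to rely on quintiles, which are no better powered.

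**Conclusion.** The point holds as a mismatch between the aim in 4.0 and the analysis in 11.3. No planned output shows the HCT effect by comorbidity, age or any other clinical profile, and propensity quintiles do not fill the gap.

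The sample supports only modest answers: about 25-37% power for a 13-point difference in benefit, and a detectable ratio of hazard ratios of about 1.8-2.1. These figures assume comparison OS of 20-50%, a two-level modifier of 25-50% prevalence that is equally common in both treatment groups, and 400-480 deaths. They also ignore the time-dependence that section 11.1 says will reduce power, and a three-level HCT-CI factor would be less precise still.

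Two stronger readings should be avoided. The overall HCT comparison is not invalidated, and the documents do not show that the HCT effect actually differs by comorbidity score. HCT-CI is nevertheless the natural first candidate. In the older nonmyeloablative series in section 3.3 it predicted NRM, while outcomes did not differ significantly by age group.

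**What to change.** In the 11.3(2)(i) models for OS and NRM:

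- Pre-specify an interaction of HCT with HCT-CI group at enrollment (0, 1-2, 3 or more) as the main effect-modification analysis.
- Add HCT by age with age continuous, or estimate it within patients aged 60 or over and separately within scores of 3 or more. State that the cohort has no patients under 60 with scores of 0-2.
- In each level, report the HCT hazard ratio and the 2-year absolute difference with confidence intervals, whatever the interaction P value. Say how the absolute difference is derived, given that HCT is time-dependent. Label these results exploratory.
- Use propensity quintiles to describe selection, not to identify who benefits.
- State the limited power, with the assumptions above.
- Give objective 5.2.1.3 a matching analysis, or say that it will be descriptive.

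If the sponsor does not want this, the wording in 4.0 should be narrowed to the overall comparison, but that gives up a question the collected data can partly address.

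The cost is some SAP text and modest programming. HCT-CI and age are already collected (8.1.4 and 8.1.1). The downside is wide stratum intervals and a few extra comparisons.

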5.0 OBJECTIVES

5.1 Primary objectives

- 5.1.1 Feasibility of allogeneic HCT in older and medically infirm patients with AML
 - 5.1.1.1 Estimating the probability of undergoing allogeneic HCT among older and medically infirm AML patients compared to younger and relatively healthier patients.
 - 5.1.1.2 Comparing the characteristics of patients who did versus did not proceed to allogeneic HCT.
- 5.1.2 Comparison of outcomes among prospectively enrolled older and medically infirm AML patients given allogeneic HCT versus induction therapy
 - 5.1.2.1 Non-relapse mortality (NRM), overall (OS), and disease-free survival (DFS).
 - 5.1.2.2 QOL

5.2 Secondary objectives

- 5.2.1 Among a subset of patients, studying the impacts of some pulmonary function tests (diffusion capacity of carbon monoxide, and forced expiratory volume in one second) and plasma biomarkers (C-reactive protein, albumin, ferritin, and vitamin D) on:
 - 5.2.1.1 Overall mortality at 8 weeks after induction therapy
 - 5.2.1.2 Feasibility of allogeneic HCT
 - 5.2.1.3 Comparison of outcomes between allogeneic HCT versus conventional therapy

5.3 Tertiary objectives

- 5.3.1 Preliminary therapy data will be used to develop standardized criteria for the definitions of “intensive” and “less-intensive” treatments. Physicians from around the world will be surveyed about their opinion of the intensity of regimens.

Protocol 2368.00

- 5.3.2 Project results will be disseminated per funding agency's request using novel methods. Methods will include social media, websites, videos, and newsletters. Patients may be asked to appear on video. All methods have the possibility of being published or mentioned in publications.
- 5.3.3 Among a subset of patients admitted to the ICU at any time point after induction chemotherapy, evaluation of risk factors associated with 90-day and overall survival after ICU admission. Rates of palliative care referrals in patients with and without ICU admissions will be examined.
- 5.3.4 Comparison of outcomes between patients with secondary AML and patients without secondary AML.

6.0 PATIENT ELIGIBILITY

6.1 Inclusion Criteria

- 6.1.1 Patients with new diagnoses of non-M3 AML (See study document '2008 WHO Classification of AML') or high-risk MDS, (See study document '2008 WHO Classification and Criteria for MDS') myeloproliferative neoplasms (MPN), or myelofibrosis (MF) (MDS, MPN, or MF showing 10% or more blasts in bone marrow) who:
 - 6.1.1.1 Present for an AML-like treatment that could plausibly produce a complete remission (CR); for example intensive induction chemotherapy, low dose single agent chemotherapy, hypomethylation agent, or a similar therapy
 - 6.1.1.2 Potentially possible to retrieve follow-up records from the collaborating institution or treating primary care physician.
- 6.1.2 Patients with primary refractory or first relapse presenting for salvage chemotherapy will be allowed
- 6.1.3 Patients of ≥ 18 years of age and are being treated by the adult AML service.
- 6.1.4 Able to speak and read English.
- 6.1.5 Willing and able to provide informed consent.

6.2 Exclusion Criteria

- 6.2.1 Patients of ≤ 17 years of age or who are ≥ 18 and receive treatment under the pediatric AML service.
- 6.2.2 Patients older than 80 years
- 6.2.3 Patients with < 6 months projected survival due to active second malignancy or other medical problem.

7.0 ENROLLMENT

Typically, AML-specialized physicians at SCCA and collaborating institutions first interact with the patient in a consultation session for a newly diagnosed or relapsed AML or AML-like presentation. During the initial consultation session, physicians explain the diagnosis of AML, risks and benefits of induction therapy versus no treatment. It is common that available clinical trials for induction therapy are presented to the patient during the initial consultation. In such setting it will be appropriate for physicians to approach eligible patients about their potential interest in the observational study. Patients could be approached for study participation by healthcare providers (as part of the consenting conference) or by the protocol research coordinator. To facilitate, this discussion, the physician may use a prepared one-page document explaining the study or leave a prepared one-page letter with the patient that explains the study (See study documents 'Talking Points and Physician-Facilitated Study Letter'). Explanation of the study could be briefed by the physicians and then further explained by the study coordinator for patients treated at the SCCA and by the collaborators' staff at the other sites. Additionally, the study coordinator will be available by phone or email to answer any additional questions raised by patients at any of the collaborating sites.

Protocol 2368.00

The study procedures will be outlined and patients will have an opportunity to ask questions. If necessary, discussion about the study may take place by telephone. Signed informed consent is required for enrollment. If the patient is unable to provide written informed consent prior to questionnaire completion because of logistic limitations, questionnaires could be completed on the basis of verbal consent (See study document ‘Study Letters and Phone Script for Consenting). However, no research data will be entered into the database until written consent is documented. We expect the need for verbal consent prior to written consent to be rare; priority will be to consent right following a clinic visit. If recruitment cannot be completed in person, priority will go to contacting the patient over the phone, using the phone script. During the consenting process, if the patient indicates they do not want to participate in all aspects of the study, they can mark this on the consent form. Patients that fail to consent to the study will be asked to fill out a consent failure form to understand the reasons behind declining the study. This form will not collect any identifying information and will only record age, gender, race and ethnicity, and main reason for not wanting to consent to the study. We will keep these files in a secure database indefinitely.

Each patient’s oncologist will also participate in the study to provide their assessment of the patient’s preferences for involvement in treatment decision making, and their estimates of the patient’s chances of cure and survival. The oncologists are likely to provide estimates for several of the research participants. For their first assessment, they will be provided with a written explanation of the study. This will be considered their consent document, and by providing information on the assessment, they are consenting to participate in the study. We will not require the physician to provide written consent.

To develop standardized criteria for the definitions of “intensive” and “less-intensive” treatment, we will conduct a survey of renowned experts specializing in the treatment of acute myeloid leukemia (AML). Experts will be approached by email with a link to a brief survey using the Research Electronic Data Capture (REDCap) website (see **Expert Survey**). The survey will include various treatment regimens and the participant is asked to select either “less-intensive”, “intensive”, or “unsure” for each regimen. Among those regimens chosen as “intensive”, the experts will be asked to determine whether regimens are of “high” or “intermediate” intensity. The survey will be done in two (testing and validation) samples of 40-50 experts. We seek 80% agreement rate on each regimen..

